### **Response Evaluation Criteria in Solid Tumors (RECIST) Criteria: Version 1.1**

RECIST v1.1 criteria are outlined in Appendix E of the protocol.

### **Overall Response Rate (ORR, Investigator Assessment)**

The tables below provide time point overall responses for all possible combinations of tumor responses in subjects with target and non-target lesions, with or without new lesions, per RECIST v1.1.

A summary of the overall response status calculation at each time point is presented in Table 1 for subjects who have measurable lesions at baseline, and in Table 2 for subjects who have only non-measurable (therefore non-target) lesions at baseline. For data display and analysis purposes, the “BEST” overall response for each subject from all post-baseline time point overall responses will be used. The best overall response is the best response recorded from the start of the treatment until disease progression/recurrence, or occurrence of intolerable toxicity, whatever comes first, taking, for target lesions, as reference for progressive disease, the smallest sum of diameters of target lesions recorded since the treatment started.

When no imaging/measurement is done at all at a particular time point, the subject will not be evaluable (NE) at that time point. If only a subset of lesion measurements are made at an assessment, usually the case is also considered NE at that time point, unless a convincing argument can be made that the contribution of the individual missing lesion(s) would not change the assigned time point response. Overall Response Rate (ORR) will be defined as the proportion of subjects with a best overall response of Complete Response (CR), Partial Response (PR), or Stable Disease (SD).

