 - Tumor assessment, including CT/MRI as applicable. Subjects first meeting criteria for complete response or partial response at the last on-treatment tumor assessment should have a follow-up tumor assessment at the End of Trial or Early Termination visit providing it is ≥ 3 weeks from the last prior tumor assessment in order to confirm the response based on RECIST ver. 1.1 criteria.

Blood sample for biomarker analysis will be taken within 1 day of the tumor assessment.

Subjects also receiving RX-0201

- Turn off the RX-0201 infusion pump, disconnect the infusion bag and record the volume infused in the subject's medical record and eCRF if applicable.

7.9 Safety Follow-Up Visit – Stage 1 and Stage 2

Subjects will undergo the safety follow-up visit 30 days (+ 7 days) after the subject receives the last dose of everolimus or RX-0201, whichever is administered last.

The following procedures will be performed:

- Recording of concomitant medication(s), including any anticancer therapies administered subsequent to the administration of either protocol specified medication.
- Recording of adverse event(s). Serious adverse events will be reported immediately. Any adverse event that is considered related to study drug(s) will be followed to resolution or return to baseline.
- ECOG performance status
- Vital signs resting pulse, resting respiration rate, resting blood pressure (i.e., after the subject has been seated for at least 5 minutes) and temperature measurements.
- Other Assessment(s)

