- 8 Everolimus (10 mg) will be taken at the clinic on Cycle 1 Day 1, and then at home every day thereafter
- 9 Subjects will bring all everolimus packaging (empty and full) to the clinic to determine drug compliance. For subjects receiving everolimus alone, compliance will be verified at least once per cycle when the subject returns to the site.
- 10 RX-0201 compliance will be checked at the Early Termination if the subject was receiving RX-0201 at the time of early termination.
- 11 All adverse events attributed to study drug(s) will be assessed until resolution or return to baseline
- 12 Disease assessment will occur at the end of every 2 cycles
- 13 Subjects first meeting criteria for complete response or partial response at the last on-treatment tumor assessment should have a follow-up tumor assessment at the End of treatment or Early Termination visit providing it is ≥ 3 weeks from the previous tumor assessment in order to confirm the response based on RECIST ver. 1.1 criteria
- 14 Biomarker blood samples will be collected within 1 day of the disease assessment (approximately at the end of every 2 cycles and at EOT/ET if applicable)
- 15 Tissue blocks or tissue sections from initial diagnosis or upon diagnosis of advanced metastatic disease will be available for submission to the central laboratory within approximately 4 weeks after initiation of study treatment; exceptions require written documentation of why a sample is not available and prior approval by the sponsor before randomization
- 16 Cycles 1-16 only
- 17 For subjects receiving RX-0201, one blood sample will be drawn prior to the end of infusion. If the sample draw is inadvertently missed, it can be drawn on Day 15 in a subsequent cycle.
- 18 For subjects receiving everolimus alone, the assessment may be completed by phone.

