- * Progressive Disease (PD): Appearance of one or more new lesions and/or unequivocal progression of existing non-target lesions. Unequivocal progression of existing non-target lesions is defined as: (1) overall level of substantial worsening in non-target disease such that, even in presence of SD or PR in target disease, the overall tumor burden has increased sufficiently to merit discontinuation of therapy; or (2) in the absence of measurable disease, change in non-measurable disease is comparable in magnitude to the increase that would be required to declare PD for measurable disease. Examples include an increase in a pleural effusion from 'trace' to 'large', an increase in lymphangitic disease from localized to widespread
- Not evaluable (NE) When no imaging/measurement is done at all at a particular time point, the patient is not evaluable (NE) at that time point. If only a subset of lesion measurements are made at an assessment, usually the case is also considered NE at that time point, unless a convincing argument can be made that the contribution of the individual missing lesion(s) would not change the assigned time point response

Evaluation of Best Overall Response

The best overall response is the best response recorded from the start of the treatment until disease progression/recurrence (taking as reference for progressive disease the smallest measurements recorded since the treatment started). In general, the patient's best response assignment will depend on the achievement of both measurement and confirmation criteria

Target lesions	Non-Target lesions	New Lesions	Overall response
CR	CR	No	CR
CR	Non-CR/ non-PD	No	PR

CR	NE	No	PR
PR	Non-PD or not all evaluated	No	PR
SD	Non-PD or not all evaluated	No	SD
Not all evaluated	Non-PD	No	NE
PD	Any	Yes or No	PD
Any	PD	Yes or No	PD
Any	Any	Yes	PD

CR = Complete Response; PR = Partial Response; SD = Stable Disease; PD = Progressive Disease; NE = Not Evaluable

- Patients with a global deterioration of health status requiring discontinuation of treatment without objective evidence of disease progression at that time should be classified as having “symptomatic deterioration”. Every effort should be made to document the objective progression even after discontinuation of treatment.

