## **9 Efficacy Analyses**

### **9.1 Primary Efficacy Analysis**

Tumor assessment(s) will be performed by the investigator using RECIST Version 1.1 criteria with modifications (Appendix E of the protocol) at the end of every 2 cycles

Subjects first meeting criteria for complete response or partial response at the last on-treatment tumor assessment should have a follow-up tumor assessment at the End of treatment or Early Termination visit providing it is  $\geq 3$  weeks from the previous tumor assessment.

The results will be available before the beginning of the next cycle. Radiographic tumor assessment(s) performed during the screening period will be used to prospectively identify all sites of disease present at the start of treatment. Subjects with symptoms suggestive of disease progression will be evaluated for tumor progression at the time symptoms occur.

The efficacy endpoints analyzed for this study are tumor response (complete response (CR) plus partial response (PR) according to RECIST), progression-free survival (PFS), time to response and response duration (for responders only). Progression-free survival is defined as time from first dose to the earlier of either first documented disease progression or death from any cause. Time to response is defined as time from first dose to first PR or CR (that is subsequently confirmed). Duration of response will be defined as time from first PR or CR (that is subsequently confirmed) to the earlier of either first documented disease progression or death from any cause.

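### SAP 4.3 ends the best-overall-response window at intolerable toxicity, a cut-off the protocol does not have, so it is unclear whether end-of-treatment scans after a toxicity stop count

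*SAP*

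**What the plan says.** Protocol Appendix E defines the window without reference to toxicity: "The best overall response is the best response recorded from the start of the treatment until disease progression/recurrence". SAP 4.3, under Overall Response Rate, repeats the definition but runs it "until disease progression/recurrence, or occurrence of intolerable toxicity, whatever comes first". The sentence just before that one says the best "overall response for each subject from all post-baseline time point overall responses will be used", with no cut-off. SAP 9.1.2, which specifies the analysis, takes the investigator's confirmed best response from the eCRF and mentions no toxicity limit. SAP 11 lists no changes to the protocol, although protocol 9.5.1 says changes from its planned analyses will be described in the SAP.

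For confirmation, protocol 7.8 says that subjects who first meet CR or PR at the last on-treatment assessment "should have a follow-up tumor assessment at the End of Trial or Early Termination visit providing it is ≥ 3 weeks" after the previous assessment. The note in protocol Appendix B gives the purpose: "in order to confirm the response based on RECIST ver. 1.1 criteria"; Appendix A has the same note. SAP 9.1 carries the instruction forward: these subjects "should have a follow-up tumor assessment at the End of treatment or Early Termination visit". Neither document exempts subjects who stop for toxicity, and protocol 6.9 requires the end-of-treatment evaluations whatever the reason for stopping. SAP 4.3 requires confirmation of CR or PR at least 4 weeks after the response is first met.

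**The concern.** An intolerable adverse event is one of the listed reasons for stopping treatment (protocol 3.1, SAP 5.1). For a subject who stops for that reason, the end-of-treatment scan necessarily comes after the toxicity. The plan therefore orders a scan to confirm a response, while its derivation rule for best overall response can be read as closing the window before the scan is taken.

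On that reading, response status depends partly on tolerability and not only on what the tumour did. Response rate, time to response and duration of response are the Stage 2 secondary efficacy endpoints, and all three would be exposed. The clause also gives no date for the toxicity: it could mean onset, grading or discontinuation. An onset date could fall before the first response scan and put that scan outside the window as well.

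**Working it through.** The plan states no figure on this point, so there is nothing to reproduce. The check sets the rules side by side and follows a constructed case through them.

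**1. Where each text ends the window**
- Protocol Appendix E: progression or recurrence.
- SAP 4.3, best-response sentence: progression, recurrence or intolerable toxicity, whichever is first.
- SAP 4.3, preceding sentence: all post-baseline time points.
- SAP 4.3, Confirmation of Response: a lower limit of 4 weeks and no toxicity limit.
- SAP 9.1.2: no toxicity limit.

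**2. A constructed case** (dates invented for illustration)
- PR at the end of Cycle 2: 2 × 21 = day 42. Stop for toxicity on day 62. End-of-treatment scan on day 72, still PR.
- Interval: 72 − 42 = 30 days. This meets both 3 weeks (21 days) and 4 weeks (28 days).
- Reading A, where the cut-off applies to all assessments: day 72 is after day 62, so the scan cannot be used. The subject has a PR with no usable second assessment. SAP Table 3 (PR then NE) gives SD if the minimum SD duration is met, otherwise NE.
- Reading B, where the cut-off limits only when the best response is first recorded: the PR on day 42 is inside the window, and the day-72 scan confirms it under the separate confirmation rule. The subject is a responder.

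**3. SD or NE under reading A**
- The minimum SD duration is given only as generally not less than 6 to 8 weeks, that is 42 to 56 days.
- The first on-treatment scan falls on Days 18–21 of Cycle 2, that is days 39 to 42 without delays. A response first seen there reaches at most the lower end, so SD versus NE is unsettled.
- A response first seen at the end of Cycle 4 falls at about day 81 to 84, beyond 56 days, so it becomes SD.

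**4. Effect on each endpoint under reading A**
- Confirmed CR+PR rate (SAP 9.1.2): with n = 20 (the upper size of the combination arm in SAP 6), one subject is 1/20 = 5 percentage points. The SAP's exact 95% interval has lower limit Beta(0.025; x, n − x + 1) and upper limit Beta(0.975; x + 1, n − x). If three true responders become two, 3/20 = 15% (3.2% to 37.9%) becomes 2/20 = 10% (1.2% to 31.7%). The three is an assumption.
- Rate as defined in SAP 4.3 (CR+PR+SD): unchanged if the subject falls to SD; lower by one subject only if the subject falls to NE.
- Time to response (confirmed, SAP 9.1.3) and duration of response (SAP 9.1.4): the subject drops out as a responder.
- Toxicity stop before the first scan, with PD on the end-of-treatment scan: best response changes from PD to NE. Neither is a response, and the tumour-response set is defined by a measurable baseline lesion, so category counts move but the rate does not.
- PFS (SAP 9.1.1): the censoring table places no toxicity cut-off on tumour assessments, so nothing changes. The PD in the previous case would count as a PFS event while best response reads NE.

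**The case against.** The strongest reply is that the clause does not have to remove anything. It limits when the best response is recorded; confirmation is a separate rule with no toxicity limit; and SAP 9.1.2, which drives the tables, uses the investigator's confirmed response from the eCRF without the cut-off. Reading B is therefore a fair reading of the text. This stands. A reader might infer that the SAP definitely discards the confirming scan of every subject who stops for toxicity, and the documents do not support that.

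A second reply concerns size. An affected subject must first respond at the last on-treatment scan, stop for intolerable toxicity, and have an end-of-treatment scan at least 4 weeks after the response was first met. The documents give no count of such subjects and no expected response rate. A reader might multiply the 5 points by two or three subjects and quote a shift of up to 15 points; that would rest on an assumption alone. The denominator may also be below 20, because the tumour-response set requires a measurable baseline lesion.

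Third, these are secondary endpoints in a small open-label stage that no longer randomizes, and SAP 7.3.5 calls any inferential tests exploratory. That limits the weight of the point.

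The replies do not remove the conflict. SAP 4.3 is the derivation rule for best overall response, one plain reading of it departs from the protocol, and SAP 11 does not say so.

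**Conclusion.** The point holds as an undeclared and internally inconsistent derivation rule. SAP 4.3 adds a toxicity cut-off that Appendix E lacks, and one plain reading drops a confirming scan that the plan itself orders. On that reading each affected subject leaves the confirmed CR+PR rate, at 5 percentage points per subject if the denominator is 20, and leaves the time-to-response and duration-of-response analyses. The CR+PR+SD rate of SAP 4.3 changes only if the subject falls to NE. The number affected is unknown, and under the other reading it is zero. It should not be inferred that the primary endpoint is compromised: PFS does not use this window.

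**What to change.** In SAP 4.3, delete the toxicity condition and the words that follow it in that clause, so that the window ends at progression or recurrence as in protocol Appendix E. Add one sentence stating that end-of-treatment and early-termination tumour assessments count for best overall response and for confirmation, whatever the reason for stopping treatment. If the sponsor wants to keep the cut-off, define its date, justify it, and declare it in SAP 11.

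Separately, reconcile the 3-week interval in protocol 7.8 and SAP 9.1 with the 4-week interval in SAP 4.3. The deletion does not rescue scans taken at 3 to under 4 weeks, which still fail the SAP's confirmation rule.

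The cost is a few sentences of SAP text before database lock. No new data are needed, because the assessments are already scheduled.

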9.5.2.3 Time to Event Analyses

The detailed statistical analysis methods for each endpoint will be described in the statistical Analysis Plan (SAP). The Kaplan-Meier method will be applied to the following time to event endpoints:

- Progression-Free Survival: The time from first study dose to the first observation of disease progression (as classified by RECIST ver. 1.1) or death due to any cause.
- Time to response: The time from first study dose to the first observation of a complete or partial tumor response that is subsequently confirmed.
- Duration of response: The time from the first observation of a complete response or partial tumor response (whichever comes first) to the subsequent time of disease progression or death (whichever comes first) will be calculated as the duration of response for each subject.

Kaplan-Meier estimates and 2-sided 95% confidence interval for landmark times by 6-week intervals will be produced for the endpoint of progression-free survival time. Descriptive statistics for the duration and time to response for the responding subjects will be calculated.

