9.5.2.4 Tumor Response by RECIST ver. 1.1

Tumor response data will be reported descriptively in the form of listings for all subjects in Stage 2. For each treatment group, the objective response rate will be determined and estimated using RECIST ver. 1.1 (see Appendix E for details).

The overall tumor response at any scheduled time points post the first dose of study specified treatment with missing data will be assumed to be a non-responder (i.e., not a confirmed complete or partial response). Subjects without at least one uni-dimensional measurable lesion per the modified RECIST ver. 1.1 criteria will be excluded from the analyses. For each

treatment group in Stage 1 and Stage 2 of the study, the proportion of subjects with an objective response (a confirmed complete or partial response) will be presented.

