### **Duration of Response**

The duration of response will be the time from first documented response (CR or PR) until the earlier of either first documented tumor progression (PD) or death from any cause. Subjects achieving a CR or PR, who are alive without progression, are lost to follow up, or who have died without report of

progression as of the time of analysis will be censored at the date of last response assessment or last date on study, whichever is earliest.

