### 9.1.2 Best Overall Response (per eCRF)

Best overall response as assessed by the Investigator (with confirmation required for CR and PR) will be determined by RECIST criteria v1.1 per the eCRF and used in data display and analyses. The responses, listed from best to worst will be: complete response (CR), partial response (PR), stable disease (SD), progressive disease (PD), and not evaluable (NE).

The number and percentage of subjects in each category of best response and best Overall Response Rate (CR + PR) will be summarized for RX-0201 in combination with everolimus, and groups combined. The corresponding 95% confidence intervals will be computed by treatment group using the Clopper-Pearson method for calculating the exact binomial intervals.

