### **9.1.4 Duration of Response**

Duration of response (DoR) will be defined as the time from the first documented response (CR or PR) to either the first documented disease progression or death due to any cause whichever is first.

Subjects achieving a CR or PR, who are alive without disease progression or are lost to follow up at the time of analysis, will be censored at the date of last response assessment.

Only subjects who achieve a best response of CR or PR by the confirmed Investigator Assessment of Efficacy will be included in this analysis. The duration of response will be assessed on a subject-by-subject basis and descriptively summarized by treatment group and overall.

Kaplan-Meier curves for RX-0201 in combination with everolimus will be estimated if applicable.

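### SAP 4.3 counts stable disease in the overall response rate and censors responders who die without reported progression, against SAP section 9 and Protocol section 9

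*SAP*

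**What the plan says.** **Response rate.** The derived-variable entry in SAP 4.3 gives ORR as the proportion of subjects with a "best overall response of Complete Response (CR), Partial Response (PR), or Stable Disease (SD". SAP 9.1 lists the efficacy endpoint as "tumor response (complete response (CR) plus partial response (PR) according to RECIST". SAP 9.1.2, which specifies the table and its exact interval, says "best Overall Response Rate (CR + PR) will be summarized for RX-0201 in combination with everolimus" and requires confirmation of CR and PR. Protocol 9.5.2.4 says "the proportion of subjects with an objective response (a confirmed complete or partial response) will be presented".

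**Duration of response.** SAP 4.3 runs duration to the earlier of documented progression or death from any cause. Its next sentence lists who is censored, and the list includes subjects who "are lost to follow up, or who have died without report of" progression. The censoring date is the "date of last response assessment or last date on study, whichever is earliest". SAP 9.1.4 ends duration at "either the first documented disease progression or death due to any cause whichever is first" and censors only responders who are alive without progression or lost to follow-up, at the last response assessment. Protocol 9.5.2.3 measures duration "to the subsequent time of disease progression or death (whichever comes first".

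**Status of the differences.** Protocol 9.5.1 requires changes from the protocol's analyses to be described in the SAP. SAP section 11 lists none.

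**The concern.** Response rate and duration of response are Stage 2 secondary endpoints, and the SAP holds two rules for each. Section 4.3 is where derived variables are specified, so a programmer could reasonably build from it. The SAP states no order of precedence between 4.3 and section 9.

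Both 4.3 rules push the result in the favourable direction. A rate that includes stable disease, reported under the ORR label, would be read as tumour shrinkage. Censoring deaths treats a responder who died as if the response might have continued. Leaving the choice open until data are in hand also invites the question of whether the definition was picked after seeing the results.

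**Working it through.** The plan gives no target or precision figure for ORR or duration of response, so there is no stated number to reproduce. The check is a comparison of the texts, followed by illustrations of size.

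**1. Response rate, side by side**

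| Place | Counted as response | Confirmation |
|---|---|---|
| SAP 4.3, ORR entry | CR, PR, SD | Separate 4.3 paragraph, for CR and PR |
| SAP 9.1 | CR, PR | Stated for time to response and duration |
| SAP 9.1.2 | CR, PR | Required |
| Protocol 9.5.2.4 | CR, PR | Required |

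In SAP Table 3 (best overall response), PR followed by SD becomes SD, and PR followed by PD becomes SD if the minimum SD duration is met. Under the 4.3 formula these unconfirmed responders still count, so confirmation no longer filters them out.

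**2. Duration of response, side by side**

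| Place | Death without reported progression |
|---|---|
| SAP 4.3, event sentence | Event |
| SAP 4.3, censoring sentence | Censored |
| SAP 9.1 and 9.1.4 | Event |
| Protocol 9.5.2.3 | Event |

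A death after documented progression can never be the ending event, because progression came first. Deaths without documented progression are the only deaths that can be events, and these are the ones the second sentence censors. It therefore cancels the first. The PFS entry in 4.3 has no such clause, so the same death could be a PFS event and a censored duration.

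**3. Size for ORR**

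Inputs: n = 20 (Protocol 3.3, the upper limit for the combination arm); two-sided 95% Clopper-Pearson interval (SAP 9.1.2); responder and SD counts assumed.

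Lower limit = Beta quantile(0.025; x, n − x + 1); upper limit = Beta quantile(0.975; x + 1, n − x).

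- CR+PR, x = 2: 2/20 = 10%, interval 1.2% to 31.7%.
- CR+PR+SD, x = 2 + 10 = 12: 12/20 = 60%, interval 36.1% to 80.9%.
- Over 1 to 4 responders and 8 to 12 SD: 5% to 20% against 45% to 80%.

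Rough ceiling for CR+PR+SD, assuming exponential PFS with the Protocol 9.3 medians (9 and 4.5 months), S(t) = 2^(−t/median) and a month of 30.44 days:

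- SD needs 6 weeks (42/30.44 = 1.380 months): 2^(−1.380/9) = 0.899 for the combination; 2^(−1.380/4.5) = 0.809 for everolimus.
- The 12-week scan governs (84/30.44 = 2.760 months): 2^(−2.760/9) = 0.809; 2^(−2.760/4.5) = 0.654.

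Not-evaluable subjects lower these.

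**4. Size for duration of response**

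Let a share q of ending events be deaths without documented progression, with constant independent hazards and total hazard λ. Censoring those deaths leaves hazard (1 − q)λ, so the median is multiplied by 1/(1 − q). For q = 0.10, 0.20 and 0.30 (assumed) this gives 1.11, 1.25 and 1.43. The gap between last scan and death is ignored.

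Four assumed responders: progression at 3 months, death without progression at 4 (last scan 3.5), progression at 6, ongoing at 8.

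- Death as event: the curve is 0.75 at 3, 0.50 at 4, 0.25 at 6.
- Death censored at 3.5: 0.75 at 3, then 0.75 × (1 − 1/2) = 0.375 at 6.

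Taking the median as the first time the curve is at or below 0.50, it moves from 4 to 6 months. Averaging over the flat step in the first case would give (4 + 6)/2 = 5, with the same direction.

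**5. Smaller mismatches**

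- Censoring date: the 4.3 rule takes the earlier of two dates; 9.1.4 uses the last response assessment only.
- Time to response: the 4.3 entry does not say the response must be one later confirmed; SAP 9.1, SAP 9.1.3 and Protocol 9.5.2.3 do.
- Protocol Appendix E ends duration at recurrence or progression and does not mention death.

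**The case against.** The strongest reply is that the operative rule can be inferred. SAP section 11 declares no changes, so Protocol 9.5.2.3 and 9.5.2.4 stand; SAP section 9 agrees with them; and 9.1.2 is where the reported rate and its interval are specified. That is a good reason to settle the conflict in favour of section 9. It does not remove the conflict, because the inference is written nowhere.

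The smaller mismatches carry little weight, and this part of the reply mostly stands. The confirmation paragraph in SAP 4.3 already implies that CR and PR are confirmed. A last response assessment will normally fall on or before the last date on study, so the two censoring dates nearly always coincide. Appendix E reproduces general RECIST text, and Protocol 9.5.2.3 defines duration for this trial. These are clarifications to make in the same edit.

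The illustrations also have limits. The everolimus arm is about 3 subjects, so its rate can only be 0, 33, 67 or 100%, and the ceilings for that arm say little. With only 2 responders a Kaplan-Meier median is barely meaningful. SAP 9.1.4 makes subject-by-subject description the main report, with curves only if applicable, and plain mean durations are not raised by the censoring.

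One further remark is sound but separate: SAP 4.3 wants confirmation at least 4 weeks after first response, while SAP 9.1 and Protocol 7.8 plan the end-of-treatment confirmatory scan at 3 weeks or more. A response confirmed between 3 and 4 weeks could be classed either way.

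**Conclusion.** The concern holds. SAP 4.3 contains two wrong derivation rules: an ORR that includes stable disease, and a duration-of-response rule that contradicts itself on death. Both conflict with SAP section 9 and Protocol section 9, and no declared change or precedence rule resolves them.

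The consequence is conditional on 4.3 being programmed. ORR would then rise by the full stable-disease fraction, 40 to 60 percentage points for an assumed 8 to 12 of 20. The Kaplan-Meier median duration would be lengthened by about 11% to 43% if an assumed 10% to 30% of ending events are deaths without documented progression, and not at all if there are none. If section 9 is followed, no reported number changes. Primary PFS and the sample size are unaffected. This should be fixed, but it does not threaten the trial's main result.

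**What to change.** In SAP 4.3:

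- **(a)** Define ORR as the proportion with confirmed CR or PR. If CR+PR+SD is wanted, report it separately as the disease control rate.
- **(b)** Delete from the duration-of-response censoring sentence the words covering responders who died without reported progression, so that these deaths are events.
- **(c)** Set the censoring date to the last response assessment, as in 9.1.4.
- **(d)** State in the time-to-response entry that the response is one subsequently confirmed, as in 9.1 and 9.1.3.
- **(e)** Note that Protocol 9.5.2.3 governs over Appendix E for duration of response.

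Items (a) and (b) are the substance; (c) to (e) are tidying. The 3-week and 4-week confirmation intervals should be reconciled in the same revision.

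The cost is SAP wording only, if done before programming or database lock. It needs no new data, no added analysis and no sample-size change.
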